## 9.2 SECONDARY ENDPOINTS: EFFICACY

The long-term effects of alemtuzumab will be examined by summarizing from baseline (date of the inclusion in the initial studies: CAMMS223, CAMMS323 or CAMMS324) through the last study visit the following efficacy endpoints:

- Annualized relapse rate (ARR).
- Proportion of patients relapse free.
- Change over time in Expanded Disability Status Scale (EDSS) scores.
- Change over time in brain imaging findings to include:
  - Number of Gadolinium (Gd)-enhancing, and new Gd-enhancing lesions.
  - Number of new/enlarging T2 lesions.
  - Number of new T1 (and new hypointense T1) lesions.
  - T1 and T2 lesion volume.
  - Brain Parenchymal Fraction (BPF).
- Change over time in self-reported quality of life (QoL) as assessed by the Medical Outcome Study (MOS) 36-Item Short-Form Health Survey (SF-36) Version 2.
- Change over time in the Functional Assessment of Multiple Sclerosis (FAMS), and
- Change over time in the EuroQoL in 5 Dimensions (EQ-5D).

## 9.3 OTHER ENDPOINTS

The modified HRUQ/HRPQ will be administered to obtain pharmaco-economic data.

## 9.4 APPROPRIATENESS OF MEASUREMENTS

The assessments used in this study are standard for evaluation of therapy in patients with MS.

## 9.5 SAFETY MEASUREMENTS

### 9.5.1 Adverse events

Collection of AEs (refer to [Section 10.4](#) for details) spontaneously reported by the patient or observed by the Study Investigator extends from the signing of the informed consent form until the end of the study visit. All reported AEs will be recorded in the patient's records and in the e-CRF at all visits.

Patients will be asked to volunteer information concerning AEs with a non-leading question such as: "How have you been since your last visit?"

An IAR is defined as any adverse event occurring during and within 24 hours of alemtuzumab infusion.

## 9.5.2 Laboratory safety variables

### 9.5.2.1 *Patients exposed to alemtuzumab within 48 months prior to inclusion in this study*

- The following parameters must be obtained at monthly intervals until 48 months after the last infusion of alemtuzumab administered in the study CAMMS03409:
  - CBC with differential (including platelet count).
  - Serum creatinine.
  - Urinalysis (minimally including determination of urine protein and red blood cells) with microscopy.
- TSH must be obtained every 3 months until 48 months after the last infusion of alemtuzumab administered in the study CAMMS03409.
- For women, a Human Papilloma Virus (HPV) screening must be performed as follows:
  - For women within 48 months follow-up at time of study transition from CAMMS03409 to TOPAZ, the date of the last alemtuzumab infusion administered in the study CAMMS03409 must be checked, and then an HPV screening performed approximately 1 year after the last infusion of alemtuzumab, and then every 12 months until 48 months safety FU is completed.

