# 1 FLOW CHARTS

## 1.1 GRAPHICAL STUDY DESIGN

- ★ Only for patients treated with alemtuzumab: monthly laboratory safety variables collection for 48 months after last infusion
  - For patients who received alemtuzumab in CAMMS03409 study less than 48 months before entering in LPS13649 study, and
  - For patients receiving retreatment with alemtuzumab during the LPS13649 study

\* After completion of 5 years of the first patient inclusion, the next scheduled visit for any patient will be performed as EOS visit.

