## 1.2 STUDY FLOW CHARTS

### 1.2.2 Re-treatment with alemtuzumab flow chart

For all the patients re-treated with alemtuzumab and for 48 months after last infusion.

|   | Prior to treatment | During 48 months |     |     |     |     |     |     |     |     |      |      |      |
|---|--------------------|------------------|-----|-----|-----|-----|-----|-----|-----|-----|------|------|------|
|   |                    | 1 M              | 2 M | 3 M | 4 M | 5 M | 6 M | 7 M | 8 M | 9 M | 10 M | 11 M | 12 M |
| Pregnancy test (in women of childbearing potential) | X                  |                  |     |     |     |     |     |     |     |     |      |      |      |
| ECG   | X                  |                  |     |     |     |     |     |     |     |     |      |      |      |
| HPV (only in women)                                 | X a     |                  |     |     |     |     |     |     |     |     |      |      | X    |
| CBC with differential (including platelet count)    | X b     | X                | X   | X   | X   | X   | X   | X   | X   | X   | X    | X    | X    |
| Serum Creatinine and LFT (liver function tests)     | X b     | X                | X   | X   | X   | X   | X   | X   | X   | X   | X    | X    | X    |
| Urinalysis with microscopy                          | X b     | X                | X   | X   | X   | X   | X   | X   | X   | X   | X    | X    | X    |
| TSH   | X b     |                  |     | X   |     |     | X   |     |     | X   |      |      | X    |
| Study Investigator review of labs                   | X                  | X                | X   | X   | X   | X   | X   | X   | X   | X   | X    | X    | X    |

Monthly safety laboratory assessment will be performed in local laboratories at the patients' convenience.

- a* If not performed in the previous 12 months. In addition, an HPV screening should be performed approximately 1 year after the last alemtuzumab infusion date, and then every 12 months until the 48 months safety follow-up is completed. For women patients re-treated with alemtuzumab during the study, an HPV screening should be performed prior to re-treatment (if not performed in the previous 12 months) and then every 12 months until the 48 months safety follow-up is completed.
- b* If not performed in the previous 2 weeks. LFT includes: ALT, AST, ALP, albumin, total protein, total bilirubin, and direct bilirubin.

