## 6 STUDY DESIGN

### 6.1 DESCRIPTION OF THE PROTOCOL

This study is a Phase 3B/4, international, multicenter, open-label, non-comparative study to evaluate the long-term safety, efficacy and QoL of alemtuzumab in patients who have completed at least 48 months of the extension study CAMMS03409. In addition, impact of treatment on pharmaco-economic data will be evaluated.

Patients treated with alemtuzumab within 48 months prior to enrollment in the LPS13649 study must be followed-up at monthly intervals until 48 months after the last infusion of alemtuzumab ([Section 10.1.6.2](#)).

Scheduled visits for safety and efficacy assessments will be performed every six months. AEs and concomitant medications will be monitored continuously. Quality of life, pharmaco-economic data and brain imaging will be collected every twelve months.

Patients must contact the treating neurologist at the study site (Study Investigator) as soon as they experience any sign or symptom of MS relapse. The Study Investigator will decide on the need to schedule extra visits (unscheduled visits) to evaluate the patient's status. All procedures and assessments will be collected in the e-CRF.

At the Study Investigator discretion patients can be treated:

- Patients may receive additional courses of alemtuzumab but not sooner than 12 months from any previous alemtuzumab treatment course, or
- Patients may receive other commercial DMTs.

In the event that a Study Investigator decides to treat a patient (with alemtuzumab or another DMT) the factors contributing to the decision to treat (eg, patient is experiencing clinical and/or imaging activity) should be documented in the e-CRF.

For treatment courses of alemtuzumab the Study Investigator should refer to the safety information in the Investigator's Brochure (IB) or in the approved label in the country/region when available. All treatment courses will consist of 12 mg/day alemtuzumab intravenously infused once daily on 3 days ([Section 8.1](#)).

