### 10.1 VISIT SCHEDULE

#### 10.1.1 Visit 1: selection (D1)

This visit must be conducted within 3 months (6 months for US, see [Appendix D](#)) after completion of the Extension Study CAMMS03409. When possible, Visit 1 will be performed at the same time as the last visit of the Extension Study CAMMS03409.

Prior to any assessments, information for the patient regarding the aims and methods of the study, its constraints and risks will be reviewed with the patient and a written summary in the form of an informed consent will be given to the patient. The patient must sign the informed consent before continuing the visit. The patient will keep the same patient number as used in the Extension Study CAMMS03409.

The following items will be checked/performed and recorded:

- Informed consent signature.
- Eligibility by review of Inclusion/Exclusion criteria ([Section 7](#)).
- Date of the last infusion of alemtuzumab.
  - If the treatment was administered within the previous 48 months, the patient must be followed-up as described in [Section 10.1.6.2](#).
- Safety assessments ([Section 9.5](#)).
  - Collection of AEs still ongoing at the end of the Extension Study CAMMS03409.
  - Collection of the AE that occurred between the final visit of the CAMMS03409 study and Visit 1.
  - Collection of laboratory results, if any, performed between the final visit of the CAMMS03409 study and Visit 1.
  - Vital signs and physical examination (only if not performed and collected in the previous 3 months).
- Efficacy assessments ([Section 9.6](#)).
  - MS relapse verification.
  - EDSS (only if not performed and collected in the previous 3 months).
  - Brain imaging to include: G-MRI, MRI-T1 and MRI-T2 T1 pre- and post-Gadolinium (Gd), T2/PD, FLAIR and T1 sagittal sequences (only if not performed and collected in the previous 6 months).

- Health questionnaires: SF-36, FAMS and EQ-5D (only if not performed in the previous 3 months).
- Pharmacoeconomic assessment: modified HRUQ/HRPQ ([Section 9.7](#)) (only if not collected in the previous 3 months).
- Previous medication (from the end of the Extension Study CAMMS03409 to Visit 1 of LPS13649 study).
- Concomitant medication.

An appointment should be scheduled for next visit in 6 months ( $\pm 14$  days).

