  - Consider permanently discontinuing the LEMTRADA infusion if the patient shows clinical symptoms suggesting development of a serious adverse event associated with the infusion (myocardial ischemia, hemorrhagic stroke, cervico-cephalic arterial dissection or pulmonary alveolar hemorrhage).
  - Implement appropriate measures for patients at risk of venous thromboembolism: repeated ambulation during infusion and/or compression stockings.
- Post-infusion: Observation and education of patients.
  - Observation for infusion reactions is recommended for a minimum of 2 hours after LEMTRADA infusion.
  - Patients with clinical symptoms suggesting development of a serious adverse event temporarily associated with the infusion (myocardial ischemia, hemorrhagic stroke, cervico-cephalic arterial dissection or pulmonary alveolar hemorrhage) should be closely monitored until complete resolution of the symptoms. The observation time should be extended as appropriate.
  - Patients with persistent blood pressure elevation should be referred to an appropriate medical facility for continued monitoring and treatment.
  - The patients should be educated on the potential for delayed onset of infusion associated reactions and symptoms and signs of cardiovascular or cerebrovascular events, and instructed to report symptoms and seek appropriate medical care.

For monitoring potential risk of autoimmune hepatitis, liver function test must be performed for patients who newly initiate retreatment of alemtuzumab, LFT to be performed prior infusion of retreatment as baseline, and monthly for 48 months after the last infusion of retreatment of alemtuzumab. In addition, LFT may be performed at any time if clinically indicated at Investigators' discretion

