#### **10.1.6.2 Post-alemtuzumab treatment monitoring**

The following parameters must be obtained at monthly intervals ( $\pm 3$  days) until 48 months after the last infusion of alemtuzumab:

- CBC with differential (including platelet count).
- Serum creatinine.
- Liver function test (ALT, AST, ALP, albumin, total protein, direct and total bilirubin)
- Urinalysis (minimally including determination of urine protein and red blood cells) with microscopy (if not performed in the previous 2 weeks). (Please also refer to footnote in [Section 9.5.2](#)).

TSH must be obtained every 3 months ( $\pm 3$  days) until 48 months after the last infusion of alemtuzumab.

For women, an HPV screening must be performed every 12 months ( $\pm 14$  days) until 48 months safety FU is completed.

The blood and urine sampling will be performed in local laboratories at the patients' convenience. Results must be sent to the Study Investigator. The Study Investigator must review laboratory data as soon as the results are available and they will be recorded in the e-CRF.

If the 48-month period of safety follow-up continues after the study ends, the patient will be followed by their physician in a regular healthcare setting, in line with the local approved Risk Minimization Plan for alemtuzumab, until the 48-month period is completed.

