#### **2.1.4.3 Laboratory safety variables**

Clinical laboratory data consists of blood analysis, including hematology, clinical chemistry, and urinalysis. Clinical laboratory values after conversion will be analyzed into standard international units and international units will be used in all listings and tables.

For patients exposed to alemtuzumab within 48 months prior to inclusion in this study, samples for clinical laboratories will be taken at monthly for CBC with differential (including platelet count), serum creatinine, liver function and urinalysis. TSH must be obtained every 3 months and HPV test should be performed yearly until 48 months after the last infusion of alemtuzumab administered in the study CAMMS03409.

For patients exposed to alemtuzumab during this study, pregnancy test, HPV test must be obtained before the infusion in TOPAZ study if they were not done within 12 months prior to the treatment. CBC with differential (including platelet count), serum creatinine, TSH, liver function test (ALT, AST, ALP, albumin, total protein, direct bilirubin and total bilirubin) and urinalysis (minimally including determination of urine protein and red blood cells) with microscopy are also required to be assessed before alemtuzumab infusion if they were not assessed within 2 weeks prior to treatment. Samples for CBC with differential (including platelet count), serum creatinine, liver function and urinalysis will be analyzed monthly. The TSH will be performed quarterly. The HPV test will be performed yearly. In addition, unscheduled liver function tests may be performed at any time if clinically indicated at Investigators' discretion.

The laboratory parameters will be classified as follows:

- Hematology
  - **Red blood cells and platelets and coagulation:** hemoglobin, hematocrit, red blood cell count, platelet count
  - **White blood cells:** white blood cell count, neutrophils, lymphocytes, monocytes, basophils, eosinophils
- Clinical chemistry
  - **Renal function:** creatinine, creatinine clearance
  - **Liver function:** alanine aminotransferase, aspartate aminotransferase, alkaline phosphatase, total protein, albumin, direct bilirubin and total bilirubin

- TSH

Urine samples will be collected minimally including determination of urine protein and red blood cells with microscopy.

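### Protocol 9.5.2.1 lists no liver function tests for patients last infused in CAMMS03409, while Protocol 10.1.6.2 and SAP 2.1.4.3 require them monthly for the same patients

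*Protocol*

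**What the plan says.** The group in question is patients whose last alemtuzumab infusion was in CAMMS03409 and less than 48 months old when they entered LPS13649.

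Protocol 9.5.2.1 is the section titled for them. It opens: "The following parameters must be obtained at monthly intervals until 48 months after the last infusion of alemtuzumab administered in the study CAMMS03409". The monthly items are blood count with differential, serum creatinine and urinalysis. TSH is every 3 months and HPV screening is yearly for women. No liver test appears. The parallel section for patients re-treated in the study, 9.5.2.2, does list monthly liver tests.

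Other text brings liver tests in for the same group:
- Protocol 6.1: "Patients treated with alemtuzumab within 48 months prior to enrollment in the LPS13649 study must be followed-up at monthly intervals", with a reference to Section 10.1.6.2.
- Protocol 10.1.1: "If the treatment was administered within the previous 48 months, the patient must be followed-up as described in" Section 10.1.6.2.
- Protocol 10.1.6.2, among the mandatory monthly items up to 48 months after the last infusion: "Liver function test (ALT, AST, ALP, albumin, total protein, direct and total bilirubin". Nothing there limits the list to infusions given during LPS13649.
- SAP 2.1.4.3, for patients exposed within 48 months before inclusion: "samples for clinical laboratories will be taken at monthly for CBC with differential (including platelet count), serum creatinine, liver function and urinalysis".

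Some text points the other way. Protocol 10.1.6 says "liver function test must be performed for patients who newly initiate retreatment of alemtuzumab". Flow chart 1.2.2 is headed "For all the patients re-treated with alemtuzumab and for 48 months after last infusion". SAP 2.5.3.1 describes the monthly liver function window in terms of re-treated patients.

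**The concern.** Two sets of mandatory instructions cover the same patients and differ on one test. A site that runs monthly liver tests satisfies every section. A site that works from 9.5.2.1 alone misses tests that 10.1.6.2 requires.

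Safety is the primary objective. ALT increase and autoimmune hepatitis are adverse events of special interest (Protocol 10.4.1.3 and Table 2), and Section 4 refers to acute liver failure requiring transplant. A silent ALT rise is found only by testing.

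The analysis is exposed too. SAP 2.4.5.3 runs the laboratory analysis in both the re-treated and the 48 months follow-up populations. Its liver-injury part gives the proportion of patients with potentially clinically significant abnormalities (PCSAs), Kaplan-Meier time to elevation, and possible Hy's law cases, and does not restrict these to re-treated patients. If sites followed different sections, these results would depend on which section each one used.

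**Working it through.** The plan states no figure to reproduce. The check compares the text and then bounds the number of tests at issue.

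**Rule for patients last infused in CAMMS03409, by section**

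| Section | Liver tests for this group |
|---|---|
| Protocol 9.5.2.1 | Not listed |
| Protocol 10.1.6.2, reached through 6.1 and 10.1.1 | Monthly, mandatory |
| SAP 2.1.4.3 | Monthly |
| Protocol 10.1.6 | Required for newly re-treated patients; this group not mentioned |
| Protocol flow chart 1.2.2, SAP 2.5.3.1 | Written for re-treated patients; this group not mentioned |

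The last row does not decide the matter. Both places describe every monthly test in re-treated terms, including blood count and creatinine, which 9.5.2.1 plainly requires in this group. The graphical design (Protocol 1.1) is neutral: it places "For patients who received alemtuzumab in CAMMS03409 study less than 48 months before entering in LPS13649 study" under monthly laboratory collection together with re-treated patients, but names no tests.

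**How the analysis is affected.** Under SAP 2.4.5 the PCSA denominator is the number of patients assessed for the parameter. Patients at a site doing no routine liver tests leave that denominator unless they are tested for cause. The Kaplan-Meier rule in SAP 2.4.5.3 dates an elevation at the midpoint between the first elevated test and the test before it, so it also relies on a regular schedule.

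**How many tests.** The document history and amendment log date the liver tests: they entered with the amended protocol of 24-Jul-2019 and became monthly on 28-Jan-2020. Subtracting 48 months, a window was still open only if the last infusion fell after 24-Jul-2015 (any liver test) or after 28-Jan-2016 (monthly tests).

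Last-infusion dates are not given, so the dates below are assumptions. Tests left = whole months from 28-Jan-2020 to (last infusion + 48 months).

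| Assumed last infusion | + 48 months | Monthly tests left |
|---|---|---|
| 28-Jan-2016 | 28-Jan-2020 | 0 |
| 23-Mar-2016 | 23-Mar-2020 | 1 |
| 30-Jun-2016 | 30-Jun-2020 | 5 |
| 31-Dec-2016 | 31-Dec-2020 | 11 |

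Study end is a second cap: first enrolment + 5 years + 6 months = first enrolment + 66 months (Protocol 6.2.2). The first-enrolment date is also not given.

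| Assumed first enrolment | + 66 months | Whole study months left after 28-Jan-2020 |
|---|---|---|
| 01-Jan-2015 | 01-Jul-2020 | 5 |
| 01-Jul-2015 | 01-Jan-2021 | 11 |
| 23-Mar-2016 | 23-Sep-2021 | 19 |

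The gap per patient is the smaller of the two. With first enrolment on 01-Jan-2015 it is 0, 1, 5 and 5 for the four infusion dates. With either later enrolment date it is 0, 1, 5 and 11. Under 9.5.2.1 alone the number of scheduled liver tests is 0 throughout.

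**The case against.** The strongest reply is that liver tests were meant only for re-treated patients, so 9.5.2.1 is right and the loose text is elsewhere. Protocol Section 4 introduces periodic liver tests in connection with re-treatment during the trial, 10.1.6 ties them to newly started re-treatment, and 9.5.2.2 lists them for patients exposed during the study. The amendment tables record liver-test changes against 1.2.2, 9.5.2.2, 10.1.6, 10.1.6.1, 10.1.6.2 and Appendix A, never 9.5.2.1. This reading is tenable and the documents do not exclude it. It moves the error without removing it: 10.1.6.2, as reached from 6.1 and 10.1.1, and SAP 2.1.4.3 would then be wrong.

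A second reply is that 9.5.2.1 forbids nothing and two cross-references lead to 10.1.6.2, so only a site that overlooks both would go astray. That is fair, but 9.5.2.1 is where a site would look first for these patients, and it reads as a complete list.

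A third is that the harm to the analysis is limited. Untested patients are not counted as normal, and SAP 2.4.5 calls the safety analysis essentially descriptive. This stands: no test or decision rule is affected. What suffers is the completeness and comparability of a descriptive safety result.

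A fourth is that the size rests on assumed dates. This also stands. The figure of 11 needs a last infusion as late as 31-Dec-2016. Ethics approval of the amendment (Protocol 15) would usually delay the start of testing and lower the count further.

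**Conclusion.** The inconsistency is real and lies in the current text. For patients last infused in CAMMS03409 within 48 months of entry, Protocol 9.5.2.1 schedules no liver tests, while Protocol 10.1.6.2 and SAP 2.1.4.3 schedule them monthly. The documents do not settle which was intended.

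Its reach is uncertain. The number of patients is not given and may be small or zero. Under the assumed dates the gap is 0 to 11 in-study monthly tests per affected patient. The documents do not show that sites differed, and no effect on any estimate is claimed. The point is still worth correcting. It concerns an event of special interest under the primary safety objective, and the liver outputs for the 48 months follow-up population cannot be interpreted until the plan says whether routine liver data are expected there.

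**What to change.** **If liver tests are intended for this group:** add monthly liver function tests to Protocol 9.5.2.1 to match 10.1.6.2 and SAP 2.1.4.3. Extend the wording of Protocol 10.1.6, flow chart 1.2.2 and SAP 2.5.3.1 to patients still inside the 48-month window from CAMMS03409.

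*Cost:* wording in three protocol places and one SAP place. No visit or blood draw is added, because these patients already give monthly samples for blood count and creatinine. The seven-analyte panel and the 24-hour reporting of ALT increases are extra work only for a site that has been following 9.5.2.1 alone.

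**If routine liver tests are intended for re-treated patients only:** state that exception in Protocol 10.1.6.2, remove liver function from the sentence on previously exposed patients in SAP 2.1.4.3, and limit the liver-injury analysis in SAP 2.4.5.3 to the re-treated population.

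*Cost:* wording in one protocol place and two SAP places, and the loss of the planned liver-injury outputs for the 48 months follow-up population.

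In either case, keep unscheduled liver tests in the PCSA analysis, as SAP 2.4.5 and 2.5.4 already provide.
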